6.8.2.5 Graphical Presentation of Primary Efficacy Data

Least squares mean plots of change from baseline in peak VO₂ assessments over time, along with the corresponding 95% confidence intervals will be presented by treatment group.

In addition, cumulative distribution function (CDF) plots of the percent change from baseline values at Week 12 will be plotted by treatment group. To aid in the interpretation of the graphical representation of the CDF across treatments, a two-sample Kolmogorov-Smirnov test will be conducted.

6.8.3 Secondary Efficacy Endpoints

The following secondary efficacy endpoints will be used to evaluate the effect of praliciguat on exercise and functional capacity.

- Change from baseline in 6MWT distance at Week 12. 6MWT is a simple assessment of everyday functional capacity and provides a global evaluation of the organ/physiologic systems involved in exercise. The distance, in meters, travelled in 6 minutes, measured at approximately the same time of day will define the endpoint.
- Change in ventilatory efficiency as defined by VE/VCO₂ slope (minute ventilation/carbon dioxide production) obtained from CPET at Week 12. These values will be provided by an independent central CPET Core Lab
- CPET Responders, defined as patients who improve by at least 1.5 mL O₂/kg/min in peak VO₂ from baseline to Week 12. Patients who are hospitalized or who die due to heart failure during the study treatment period or who are missing Week 12 postdose values will be considered non-responders.

6.8.4 Exploratory Efficacy Endpoints

6.8.5 Analytical Approach for Secondary and Exploratory Efficacy Data

All secondary and exploratory efficacy analyses will be conducted using the Evaluable Population.

Analyses of change-from-baseline efficacy endpoints will be conducted using the same methods as the primary efficacy analysis. Analyses of percent-change-from-baseline will be performed on rank-transformed data. [REDACTED]

All responder and remitter efficacy endpoints will be analyzed using Cochran-Mantel-Haenszel (CMH) test controlling for the baseline stratification factors, atrial fibrillation status, and baseline peak VO₂ (< 60% or \geq 60%). The number and percentage of responders for each treatment group

along with exact (Clopper-Pearson) 95% confidence intervals will be presented for responder rates. Difference in the proportion of responders between the 40 mg praliciguat dose group and the placebo group, controlling for the stratification factors, as well as the CMH estimates of odds ratios and p-values will be presented along with the corresponding 95% CIs for differences in responder rates using the normal approximation to the binomial distribution. P-values associated with the CMH test will also be presented.

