3.4.2 Early Termination Procedures

Patients who discontinue study drug for any reason should complete the assessments required at the End of Treatment Visit at the time of their discontinuation and should complete the Follow-up Visit 28 ±7 days after their final dose of study drug. If the End of Treatment Visit occurs more than 7 days after the patient's final dose of study drug, the PK blood draw can be reduced to 1 sample.

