4.2 SECONDARY ENDPOINTS

4.2.1 Secondary Efficacy

- Change from baseline in 6MWT distance at Week 12
- Change in ventilatory efficiency as defined by VE/VCO₂ slope (CPET) at Week 12
- CPET Responders (Responders are subjects who improve by at least 1.5 mL O₂/kg/min in peak VO₂ from baseline to Week 12. Subjects who are hospitalized or who die due to heart failure during the study Treatment Period are considered nonresponders.)

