5.9.3 Analyses on the Secondary Efficacy Endpoints

All secondary and exploratory analyses will be performed on the Evaluable Population and a subgroup of the Evaluable Population excluding patients with permanent or persistent atrial fibrillation at baseline.

ANCOVA models described in Section 5.1.1 will be used to compare the 40-mg IW-1973 group with the placebo group on the following secondary endpoints.

- Change from baseline in 6MWT distance at Week 12
- Change in ventilatory efficiency as defined by VE/VCO₂ slope (CPET) at Week 12

Proportions of responders based on CPET will be compared using a responder analysis as described in Section 5.1.2.

Details of other analysis, such as exploratory analysis [REDACTED]

[REDACTED]

[REDACTED]

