5.4 HANDLING OF DROPOUTS OR MISSING DATA

All available data will be included.

For ANCOVA analyses, patients with missing change from baseline values will be excluded. No imputation will be performed for missing observations.

For responder analyses, all patients will be included. Patients with missing postdose data at an assessment timepoint will be treated as non-responders for that assessment timepoint

All safety and tolerability data will be summarized and analyzed when data values are available for a patient. Data handling for missing dates and other key safety data are described in Section 8.

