6. ANALYSIS METHODS

6.1 ANALYSIS POPULATIONS

The following populations will be defined for this study:

- **Screened Population:** All screened patients who have signed the informed consent form for the study and received a patient identification number.
- **ITT Population:** All randomized subjects. Patients in this population will be evaluated according to the treatment group they were assigned to at Randomization. However, all summary tables and efficacy analyses performed on this population will only include the treatment groups (placebo and 40 mg praliciguat) specified in the final amended protocol, unless specified otherwise.
- **Safety Population:** All randomized patients who take at least 1 dose of study drug. The Safety Population will be used for all safety assessments. In the event that a subject receives the wrong treatment, the actual treatment will be used. If a patient received more than 1 treatment, then the patient's data will be summarized according to the treatment they received for the longest duration. All summary tables performed on this population will only include the treatment groups (placebo and PRL 40 mg) included in the final amended protocol, unless otherwise specified.
- **Modified Intent-to-Treat (mITT) Population:** All patients in the ITT Population who take at least 1 dose of study drug and have at least 1 evaluable baseline measurement.
- **Evaluable Population:** All patients in the mITT who complete 8 weeks of dosing (± 3 days) and have at least 1 evaluable postbaseline assessment and did not have a dose reduction. Other criteria, such as major protocol deviations that might have a potential impact on efficacy evaluations (see Section 6.2), may be established and reviewed before database lock and unblinding. The Evaluable Population will be the primary analysis population for the efficacy assessment.
- **PK Population:** All randomized patients who take at least 1 dose of praliciguat and have at least 1 postdose assessment with measurable PK concentration levels.

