8. DATA HANDLING CONVENTIONS

8.1 END OF TREATMENT ASSESSMENT

Assessments performed at the end of treatment visit will be included in Week 8 and Week 12 evaluations as follows:

- If a patient has a missing Week 8 assessment, but has a non-missing EOT assessment, then the EOT assessment will be used as the Week 8 assessment if the EOT assessment was conducted on or after study day 50.
- If a patient has a non-missing Week 8 assessment and has a non-missing EOT assessment, then the EOT assessment will be used at the Week 12 assessment if the EOT assessment was performed on or after study day 77.

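### The CPET responder analysis removes early stoppers before its own non-response rule can count them

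*SAP*

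**What the plan says.** **Endpoint.** A CPET responder gains at least 1.5 mL O₂/kg/min in peak VO₂ by Week 12. Protocol 4.2.1 adds: "Subjects who are hospitalized or who die due to heart failure during the study Treatment Period are considered nonresponders". SAP 6.8.3 widens the non-responder group to: "Patients who are hospitalized or who die due to heart failure during the study treatment period or who are missing Week 12 postdose values".

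**Analysis set.** SAP 6.8.5: "All secondary and exploratory efficacy analyses will be conducted using the Evaluable Population". Protocol 5.9.3: "All secondary and exploratory analyses will be performed on the Evaluable Population and a subgroup of the Evaluable Population", the subgroup being patients without permanent or persistent atrial fibrillation (AF). Under SAP 6.1, Evaluable patients are those in the mITT Population who complete 8 weeks of dosing (±3 days), and who "have at least 1 evaluable postbaseline assessment and did not have a dose reduction". The dose-reduction condition is not in the definition in Protocol 5.3.

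**Missing data.** SAP 5.4: "For responder analyses, all patients will be included". Missing values are scored as non-response there, but no population is named.

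**Early stoppers.** Under Protocol 3.4.2, patients who stop study drug "should complete the assessments required at the End of Treatment Visit at the time of their discontinuation". SAP 8.1 lets an End of Treatment (EOT) value stand as Week 12 only when a Week 8 value exists and "if the EOT assessment was performed on or after study day 77".

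**mITT analyses.** SAP Table 4 repeats the primary analysis in the mITT Population, overall and without AF. No such repeat for responders appears in the legible text. Parts of SAP 6.8.4, 6.8.5 and section 7 are redacted.

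**The concern.** The endpoint definition makes certain failures count against a treatment. The analysis set then removes some of those same patients because of something that happened after randomisation. An HF death in Week 5 is a non-responder by definition, yet is absent from the analysis. A patient who stops at day 65 is kept and scored a non-responder, while one who stops at day 40 is deleted. Neither has a Week 12 value; only the stopping time differs, and the endpoint definition contains no such cut-off.

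The responder rate then describes patients who tolerated about 8 weeks of drug. The comparison between arms is exposed to any difference in early stopping. SAP 5.6 says the emphasis is on estimation, so a systematic shift in the estimate matters even though p-values are nominal.

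**Working it through.** **1. The plan's own figure.** Protocol 5.2 and SAP 4 give 184 patients, SD 2.5, difference 1.3, two-sided 5% error, 10% attrition, and 10% already randomised to 10 or 20 mg. Per arm: 184 × 0.9 × 0.9 / 2 = 74.5. The standardised difference is 1.3 / (2.5 × √(2/74.5)) = 3.17, and Φ(3.17 − 1.96) gives 88.8% power, in line with the stated figure of about 90%. No power or responder rate is given for the responder endpoint.

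**2. Responder rates implied by the planning values** (changes assumed normal):
- placebo: 1 − Φ((1.5 − 0)/2.5) = 1 − Φ(0.60) = 0.2743
- 40 mg: 1 − Φ((1.5 − 1.3)/2.5) = 1 − Φ(0.08) = 0.4681
- difference: 0.1939, or 19.4 points

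**3. Who is lost.** A patient who stops before about 8 weeks has EOT assessments at stopping, too early to count as Week 12. In the mITT Population that patient is missing Week 12 and is a non-responder. In the Evaluable Population the patient is absent.

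**4. Formulas.** Let T be the total loss in an arm and p the responder rate among patients with Week 12 data.
- mITT rate: p(1 − T)
- Evaluable rate, all loss early: p
- Evaluable rate, half the loss early: p(1 − T)/(1 − T/2), because late losses stay in and count as non-response

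With all loss early, the excess of the Evaluable difference over the mITT difference is 0.4681 × T(40 mg) − 0.2743 × T(placebo).

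**5. Results** (points; computed before rounding). The documents give only the overall 10% attrition, so loss by arm and timing are assumptions.

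| Loss, 40 mg / placebo | Timing | Evaluable | mITT | Excess |
|---|---|---|---|---|
| 5% / 5% | all early | 19.4 | 18.4 | +1.0 |
| 10% / 10% | all early | 19.4 | 17.4 | +1.9 |
| 5% / 5% | half early | 18.9 | 18.4 | +0.5 |
| 10% / 10% | half early | 18.4 | 17.4 | +0.9 |
| 8% / 12% | all early | 19.4 | 18.9 | +0.5 |
| 15% / 5% | all early | 19.4 | 13.7 | +5.7 |
| 5% / 15% | all early | 19.4 | 21.2 | −1.8 |

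**6. Break-even.** With all loss early, the excess is zero when T(placebo)/T(40 mg) = 0.4681/0.2743 = 1.71. At 10% average loss that is 7.4% on 40 mg and 12.6% on placebo.

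**7. Without AF** (planning difference 1.5): the 40 mg rate is 1 − Φ(0) = 0.5000 and the difference 22.6 points. With equal, all-early loss the excess is 0.05 × 22.6 = 1.1 to 0.10 × 22.6 = 2.3 points.

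**8. No drug effect** (27.4% in both arms): the excess is 0.2743 × (T(40 mg) − T(placebo)). It is zero for equal loss and 2.7 points at 15% / 5%.

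**9. Scale.** With about 75 per arm, SE = √((0.2743 × 0.7257 + 0.4681 × 0.5319)/75) = 0.077, giving a 95% interval of about ±15 points. About 184 × 0.9 / 2 = 83 per arm are randomised to 40 mg or placebo. At 10% loss, half of it early, about 4 per arm are removed.

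**The case against.** **The Evaluable Population is the chosen target.** It is the SAP's primary efficacy set and the sample size rests on it. On that view, the equal-loss gap is only the shrinkage that non-response scoring applies to a real difference. It is fair that the gap measures departure from an all-patient result. But the benchmark is the plan's own endpoint definition, which calls these patients non-responders.

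**With no drug effect, equal loss does no harm.** True: a false advantage then needs unequal loss, and the 1.71 ratio holds only under the planning rates. Unequal loss remains possible and cannot be ruled out before unblinding.

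**The effect is small and the endpoint secondary.** This stands for equal loss. There is no claim about type I error.

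**Peak VO₂ is already repeated in the mITT Population, and SAP 6.3 tabulates exclusions by arm.** Both help. However, the repeat carries earlier values of a continuous variable forward and does not apply the failure rule. The SAP 6.3 counts give no responder rate.

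**SAP 5.4 may already include everyone.** Read literally, it contradicts SAP 6.8.5. Read beside the ANCOVA rule that precedes it, it means everyone in the analysis set, and the gap remains. Either way the sections need reconciling.

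**Redacted text might contain the analysis.** This cannot be excluded, though the legible sentence in 6.8.5 assigns every secondary analysis to the Evaluable Population.

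**A late EOT visit could supply a Week 12 value.** For someone stopping before Week 8, that would need a delay of more than three weeks.

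**Conclusion.** The concern holds. On the legible text, patients who stop before about 8 weeks, or who have no postbaseline assessment, are excluded before the non-response rule can act. The rule is not empty: it still works for failures after about 8 weeks and for HF-hospitalised patients who stay on drug.

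Under the planning rates the shift is about 0.5 to 1.9 points with equal loss, which is small against sampling error. It ranges from +5.7 to −1.8 points in the unequal cases tried. These figures assume normal changes, all loss before Week 8 except in the half-early cases, and loss rates the documents do not supply. Dose-reduced patients, also removed by SAP 6.1, are not in the figures; the direction of that effect is unknown. This is a worthwhile, inexpensive correction to the interpretation of a secondary endpoint, not a flaw in the primary analysis.

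**What to change.** - **SAP 6.8.5:** add a CMH analysis of CPET responders in the mITT Population (placebo and 40 mg), and in its subset without permanent or persistent AF. Score HF death, HF hospitalisation and missing Week 12 as non-response; otherwise score dose-reduced patients on their observed Week 12 value. Report it beside the Evaluable analysis, which stays as planned. Protocol 5.9.3 supplies the non-AF Evaluable comparator, which SAP 6.8.5 does not name, so state it there too.
- **SAP 5.4:** name the population to which the all-patients statement refers.
- **SAP section 7:** list the added analysis.

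The cost is wording edits in two sections, one entry in section 7 and two tables, using population and AF flags already needed for SAP Table 4. No new data are required. The downside is two more nominal results to interpret, and possibly a slightly smaller responder difference.

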6.8.6 Graphical Presentation of Secondary and Exploratory Efficacy Data

Least squares mean plots of change from baseline in 6MWT, [REDACTED]
[REDACTED] assessments over time, along with the corresponding 95% confidence intervals will be presented by treatment group. [REDACTED]
[REDACTED]

In addition, cumulative distribution function plots of the percent change from baseline values at Week 12 will be plotted by treatment group.

6.8.7 Subgroup Analyses

Analysis for change from baseline in peak VO₂, 6MWT, [REDACTED]
will be performed for the each of the following subgroups:

- Gender [Male/Female]
- Baseline atrial-fibrillation strata (yes/no)
- Baseline peak VO₂ (mL O₂/kg/min) strata [$\leq 60\%$, $> 60\%$]
- Baseline NT-pro BNP (pg/mL) [≤ 300 , > 300]
- Baseline LVEF ($\leq 50\%$, $> 50\%$)
- Presence of diabetes versus non-diabetes (diagnosis made by currently treated and/or hemoglobin A1c > 6.5)

Subgroup analyses will be performed only if the total number of subjects in each treatment group within a subgroup category is ≥ 10 . ANCOVA models will be used with change from baseline as the response variable, treatment, visit, subgroup, treatment-by-subgroup interaction, treatment-by-visit interaction and baseline stratification factors as fixed effects, and the respective baseline

value as covariate. Appropriate contrasts will be specified to obtain parameter estimates for each subgroup.

6.9.1 Primary Safety Endpoints

The primary safety endpoints are the incidence of patients with TEAEs and study drug-related TEAEs. The summary and frequency tables for safety data will be by treatment group unless otherwise specified.

All adverse events (AEs) will be coded using the Medical Dictionary for Regulatory Activities (MedDRA) Version 20.0 or newer and will be classified by MedDRA system organ class (SOC), and preferred term (PT).

Treatment-emergent adverse events (TEAEs) are those AEs that started or worsened in severity after the administration of study drug.

6.9.2 Adverse Events

An overall summary table of all adverse events will be presented and include the following:

- Patients with any TEAEs,
- Patients with any TEAEs by maximum severity,
- Patients with any TEAEs related to the Investigational Medicinal Product (IMP),
- Patients with any TEAEs leading to drug withdrawn,
- Patients with any SAEs,
- Patients with any TEAEs of Clinical Interest (AECIs; see Section 6.9.2.2).

All TEAEs will be summarized for each treatment group with the number and percentage of subjects by SOC and PT; by relationship to study drug, by maximum severity. If a patient has more than 1 TEAE coded to the same preferred term, the patient will be counted only once for that preferred term by identifying those TEAEs with the highest severity (severe > moderate > mild) and the strongest causality relationship (related > not related) to study drug per investigator.

AEs will also be summarized by study period, where AEs that started during the Screening Period, Treatment Period or Follow-up Period will be presented by treatment group (placebo and 40 mg pralicipat only) for the respective period.

For presentation of AE incidence, AEs will be sorted alphabetically by SOC, and within each SOC, by decreasing incidence of PT in the pralicipat 40 mg group. An additional presentation will include a summary of TEAEs for each treatment group by PTs only, sorted by decreasing incidence of PT in the pralicipat 40 mg group.

Summary tables will also be presented for SAEs in decreasing overall PT frequency.

Listings of AEs in screen failure patients, pretreatment AEs in randomized patients, TEAEs, severe TEAEs, study drug-related TEAEs, SAEs, TEAEs leading to study discontinuation and AEs leading to death (if any) will be provided. The listings will include the dose levels that the patients are using when AEs occur.

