3. INVESTIGATIONAL PLAN

3.1 OVERALL STUDY DESIGN AND PLAN

This Phase 2, multicenter, randomized, double-blind, placebo-controlled, parallel-group study will evaluate the safety and efficacy of IW-1973 compared with placebo. The study will enroll approximately 184 adults with established heart failure and limited exercise capacity with EF of at least 40% and who have at least 2 of 4 risk factors for HFpEF (diabetes/prediabetes, hypertension, obesity, advanced age) (see [Eligibility Criteria](#)). Patients will be stratified by atrial fibrillation status and by baseline peak VO₂ (<60% or ≥60% of age- and sex-adjusted normal values with respiratory exchange ratio [RER] ≥1.0 as determined by cardiopulmonary exercise test [CPET]) and randomized in a 1:1 ratio to daily IW-1973 or placebo, as described in Section [3.5.2](#). The number of patients admitted with permanent or persistent atrial fibrillation will be limited to under 20% of target enrollment (≤36 patients).

The study will consist of 3 distinct periods, a Screening Period, a Treatment Period, and a Follow-up Period ([Figure 1](#)).

Figure 1. Study Schematic

Screening Period: The Screening Period will begin with the signature of the ICF at the Screening Visit and may last up to 45 days. At the Screening Visit, patients will undergo screening procedures to determine their initial eligibility. At the Baseline Visit, patients will return to the clinic for additional screening procedures to determine their eligibility, including CPET, vital sign measurements, and blood and urine sample collections, and to receive supplies to take home. The end of the Screening Period will coincide with the beginning of the Treatment Period. The Screening Visit may be combined with the Baseline Visit if the patient is fasted for blood and urine collections. CPET and 6-minute walk test (6MWT) must occur within the 14-day period before Randomization.

Treatment Period: The Treatment Period will begin on Day 1 at Randomization and will end after the End of Treatment Visit on Day 85 (-7/+4 days). At the Day 1 Visit, eligible patients will be stratified as described in Section 3.1 and randomized as described in Section 3.5.2 to receive daily IW-1973 or placebo for approximately 12 weeks. Dosing on Days 1 to 14 (± 3) will be BID (twice daily); dosing on Day 15 (± 3) onward will be QD (once daily).

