3.7 INDIVIDUAL STOPPING CRITERIA AND DATA MONITORING COMMITTEE REVIEWS

If any events included in [Table 5](#) are reported during the study and are judged to be both study drug related and a serious adverse event (SAE; per causality and SAE definitions in the protocol [Section [3.8.13.3](#)]), individual stopping criteria or DMC review will be triggered per the criteria in Sections [3.7.1](#) and [3.7.2](#). The inclusion of these events is based on the clinical experience with IW-1973, the prescribing information for the sGC stimulator riociguat ([23](#)), and the patient population for this study.

Table 5. Categories of SAEs Triggering Individual Stopping Criteria and DMC Review

Treatment-emergent Study Drug-related SAE Category	Number of patients to trigger DMC review
Symptomatic hypotension-related events (eg, syncope)	5
Spontaneous bleeding events (eg, hemoptysis, vaginal hemorrhage, ovarian hemorrhage, subdural hemorrhage, hematemesis, hematochezia)	2

DMC=Data Monitoring Committee; SAE=serious adverse event

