3.8.13.4 Recording Adverse Events

Adverse events will be collected and recorded from the time the patient signs the ICF at the Screening Visit through the Follow-up Visit. All AEs, regardless of the assumption of a causal relationship with study procedures or study medication, must be recorded in the patient's source documentation and subsequently on the appropriate AE page of the patient's eCRF. This record includes AEs the patient reports spontaneously, those observed by the Investigator, and those elicited by the Investigator in response to open-ended questions during the study, such as "Have you had any health problems since your last visit?"

For every AE, the Investigator must:

- Provide an assessment of the severity, causal relationship to the study medication, and seriousness of the event
- Document all actions taken with regard to the study medication (ie, no action taken, treatment temporarily interrupted, or treatment discontinued)
- Detail any other treatment measures taken for the AE, including concomitant medications and/or procedures

Pretreatment AEs will be collected from the time the patient signs the ICF until the patient receives study drug.

Laboratory abnormalities and changes in vital signs, physical examination findings, and 12-lead ECG parameters should be considered AEs and reported on the AE page of the patient's eCRF if the Investigator considers them clinically significant and/or they necessitate intervention.

Any medical condition that is present when a patient is screened and does not worsen in severity and/or frequency should be reported as Medical History and not as an AE. However, if the condition does deteriorate in severity and/or frequency at any time during the study, it should be reported as an AE.

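### SAP 6.9.2 does not limit the SAE row and the SAE preferred-term tables to treatment-emergent events, so a pre-dose SAE would count under the randomised arm; the effect is small and the fix nearly free

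*SAP*

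**What the plan says.** SAP 6.9.2 introduces the table with "An overall summary table of all adverse events will be presented and include the following". The list that follows has six rows. Those for any event, maximum severity, relationship to study drug, drug withdrawal and clinical interest are all defined on TEAEs. The remaining row is "Patients with any SAEs". Later in the same section the SAP adds: "Summary tables will also be presented for SAEs in decreasing overall PT frequency". Neither statement restricts the SAEs by onset or by study period.

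SAP 6.9.1 defines the term: "Treatment-emergent adverse events (TEAEs) are those AEs that started or worsened in severity after the administration of study drug". Seriousness plays no part in that definition, so an SAE is not treatment-emergent merely by being an SAE.

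Protocol 3.8.13.4 sets the collection window: "Adverse events will be collected and recorded from the time the patient signs the ICF at the Screening Visit through the Follow-up Visit". It also says: "Pretreatment AEs will be collected from the time the patient signs the ICF until the patient receives study drug". Under Protocol 3.1, screening "may last up to 45 days". SAP 6.9 and 6.9.1 place the safety summaries in the Safety Population, by treatment group unless otherwise specified.

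**The concern.** Taken literally, an SAE that begins and resolves between consent and the first tablet enters a between-arm safety table under the arm to which the patient is later randomised. Such an event cannot be an effect of study drug. It raises the SAE percentage in every arm, pulls any ratio that a reader forms toward 1, and adds chance variation to small counts. The SAE row is also read beside five rows that count a different set of events, and nothing in the listed row titles would tell the reader so.

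The wording looks like an oversight. Protocol 5.10.1 planned listings of drug-related AEs and of AEs leading to study discontinuation; SAP 6.9.2 changes both to TEAEs but leaves SAEs unqualified. Elsewhere the protocol uses the narrower concept: its Table 5 is headed "Treatment-emergent Study Drug-related SAE Category".

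**Working it through.** **1. Are pre-dose days inside the collection window?** Protocol 3.3 gives total participation as 109 to 165 days. Inputs: screening from Day -45 to Day -3 (Schedule of Events) and the Follow-up Visit at Day 113 ±7.
- Maximum: 45 + (113 + 7) = 165 days.
- Minimum: 3 + (113 - 7) = 109 days.

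Both stated figures are reproduced. Screening is therefore at most 45/165 = 27% of the window and at least 3/109 = 3%.

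**2. What pre-dose SAE rate is plausible?** The documents give no SAE rates, so this step rests on assumptions. Assume a placebo SAE risk of 5% from Day 1 to Day 113, and a constant hazard that also applies during screening. Undosed patients carry no drug effect, so the placebo rate is the one to use.
- Pre-dose risk over 45 days: q = 1 - 0.95^(45/113) = 0.020, or 2.0%.
- Spreading the same 5% over 120 days gives 1.9% for 45 days of screening and 0.6% for 14 days.

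The 2% figure also supposes that every patient is screened for the full 45 days and that eligibility review removes nobody, so it is an upper value under these assumptions.

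**3. Effect on the tabulated rates.** Assume true treatment-emergent SAE risks p of 10% (40 mg) and 5% (placebo), and the same independent pre-dose risk q in both arms. The tabulated risk is p + q - pq.

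| q | 40 mg | Placebo | Ratio | Difference (points) |
|---|---|---|---|---|
| 0% | 10.0% | 5.0% | 2.00 | 5.0 |
| 1% | 10.9% | 5.95% | 1.83 | 4.95 |
| 2% | 11.8% | 6.9% | 1.71 | 4.9 |

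The difference shrinks only by the factor (1 - q).

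**4. In patients.** Sample size planning assumes about 184 patients with 10% in the 10 mg and 20 mg groups: 184 × 0.9 / 2 = 82.8, about 83 per arm. At q of 1% to 2% that is 0.8 to 1.7 patients per arm with a pre-dose SAE.

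**The case against.** The strongest reply is that the SAP already intends a TEAE-based summary. SAP 8.3 introduces its counting rules as conventions for summarising TEAEs within a treatment group, and one of those rules names the overall AE summary. The SAP introduction also says that specifications for selected tables sit in a separate document, which may already apply the filter. This makes loose wording more likely than a decision to count pre-dose SAEs. A reader might infer such a decision from the text, but the documents do not establish one. Even so, SAP 8.3 does not mention SAEs, and the row it would have to govern is the one row without the qualifier. If the table specifications do filter, the SAP text still needs to agree with them.

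Second, pre-dose SAEs can be found elsewhere. SAP 6.9.2 plans AE summaries by study period, a listing of pretreatment AEs in randomised patients and a listing of SAEs. That stands as partial mitigation. However, the period summary is described for AEs rather than SAEs, covers placebo and 40 mg only, and does not change the SAE row or tables.

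Third, few patients would be affected. Screening and baseline visits may be combined and can fall one day before randomisation. Screen failures are outside the Safety Population. Exclusion criteria 1, 5 and 23 remove patients with certain recent coronary events, heart failure hospitalisations or infections. This stands, and it keeps the weight minor. It does not bring the number to zero: exclusion 5, for example, counts back from the Baseline Visit, which can precede Day 1 by up to 14 days.

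A reader might also infer three stronger claims, none of which is supported:
- **Heavier dilution.** Applying the assumed 10% active-arm rate to screening gives 1 - 0.9^(45/113) = 4.1%, and q = 4% gives 0.136/0.088 = 1.55. That assigns a drug effect to undosed patients.
- **Bias toward one arm.** Pre-dose events are independent of assignment, so any imbalance they create is chance.
- **A contradiction with Protocol Table 5.** That table sets triggers for individual stopping and DMC review. It is not a tabulation rule; it shows only that the treatment-emergent concept was available.

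**Conclusion.** The point holds with minor weight. The SAE row and the SAE preferred-term tables lack the restriction that the other five rows carry, and as written they would count a pre-dose SAE in a dosed patient under the randomised arm. With assumed true risks of 10% and 5% and a pre-dose risk of 1% to 2%, the ratio falls from 2.0 to between 1.83 and 1.71, while the difference moves from 5.0 to about 4.9 points. Those rates are illustrative; only the length of the window comes from the documents. The ratio is one that a reader might form: SAP 6.9.2 plans no SAE risk ratio, and Protocol 5.10 makes the safety analysis descriptive. No directional bias is expected. The primary safety endpoint, the incidence of TEAEs and drug-related TEAEs, is unaffected.

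**What to change.** In SAP 6.9.2, reword the row as *Patients with any treatment-emergent SAEs* and base the SAE preferred-term tables on treatment-emergent SAEs. Show pre-dose SAEs in randomised patients on a separate line or in the pretreatment listing already planned. Align the separate table specifications if they differ.

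Nothing is lost. The SAP 6.9.1 definition has no end date, so SAEs in follow-up stay in, as does an event that began before dosing and worsened in severity afterwards. The cost is a few words and one filter in the table programs, with no change to data collection. It is best done before unblinding.
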